4.7 Safety Analyses

All statistical analysis of safety outcomes will be descriptive. Safety observations and measurements include AEs, treatment-emergent AEs (TEAEs), SAEs, clinical safety laboratory tests, vital sign measurements, physical examinations, and ECGs. The incidence of AEs, TEAEs and SAEs will be summarized by cohort, severity and relationship to study product. Baseline for safety parameters is defined as Day 0 (pre-dose) measurement. If missing, the last measurement prior to the first study drug administration will be used as the baseline value.

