2. STUDY OBJECTIVES AND ENDPOINTS

2.1 Primary Objective and Endpoint

Primary Objectives	Primary Endpoints
Safety: To evaluate the safety of IV infusions of SYNT001 at different dose levels and dosing regimens in subjects with pemphigus (vulgaris or foliaceus)	Safety: The evaluation of SYNT001 safety based on vital signs, physical examinations, electrocardiograms (ECGs), clinical safety laboratory tests, the incidence of adverse events (AEs), treatment-emergent adverse events (TEAEs) and serious adverse events (SAEs) summarized by dose and dosing regimen, severity, and relationship to study drug
Dose Selection: To determine a Minimum Effective Dose (MED) of SYNT001 as assessed by (i) total IgG level nadir and (ii) the proportion of subjects that meet the criteria for response by Pemphigus Disease Area Index total activity score (PDAI)	Dose Selection: The determination of dose and dosing regimen of SYNT001 that achieves (i) total IgG level nadir decrease by $\geq 60\%$ and $\leq 90\%$ from baseline and (ii) a PDAI total activity score of $\geq 50\%$ reduction from baseline to allow further clinical development in subjects with pemphigus (vulgaris or foliaceus)

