3. STUDY OVERVIEW

3.1 Overall Study Design and Treatment Assignment

This is a multicenter, open-label safety study to determine the dose regimen of SYNT001 administered IV in subjects with pemphigus (vulgaris or foliaceus). Up to 8 subjects with a

diagnosis of pemphigus (vulgaris or foliaceus) will receive SYNT001 10 mg/kg weekly x 5 doses (Cohort 1). Up to 12 subjects with a diagnosis of pemphigus (vulgaris or foliaceus) will receive SYNT001 30 mg/kg weekly x 3 doses (Loading), followed by SYNT001 10 mg/kg every other week x 5 doses (Maintenance) (Cohort 2).

Subjects in both cohorts will complete the following periods of assessment: Screening, Treatment, and Follow-Up.

The Dose Escalation Committee (DEC) will consist of the Medical Monitor, an Independent Clinical Expert and the Sponsor Medical Lead. The DEC may request that Investigators, other experts, or members within their organization participate in the review. Additional information on the DEC’s responsibilities is provided in Protocol Section 9.5 and the DEC Charter.

An overview of the study cohorts is provided in Table 1.

Table 1. Cohort Overview

Cohort No.	No. of subjects	SYNT001 Dose	No. of Doses	Frequency of Doses
1 ^a	Up to 8	10 mg/kg	5	NA
2 ^b	Up to 12	Loading: 30 mg/kg ^c Maintenance: 10 mg/kg ^c	3 ^c 5 ^c	Weekly ^c Every other week ^{c, d}

- a. No more than 3 subjects with pemphigus foliaceus may be enrolled
- b. Two or fewer subjects with pemphigus foliaceus may be enrolled
- c. The dose, number of doses, and frequency of doses in Cohort 2 will be confirmed based on review of safety and PD evaluations, including but not limited to, dose-limiting toxicities, AEs, TEAEs, SAEs, and total IgG levels. Following Sponsor review of emerging safety, PD and efficacy data, the Loading dose may be reduced to 20 or 10 mg/kg weekly and/or the Maintenance dose may be increased to 20 or 30 mg/kg every other week and/or dose frequency may be increased to weekly.
- d. Ongoing safety and PD evaluations may result in modification of the dose and dosing regimen in Cohort 2. See Protocol APPENDIX 5 for the corresponding visit schedule.

The duration of subject participation for each cohort is as follows:

Cohort	Screening	Treatment	Follow-up	Maximum Total	
				Days	Weeks
1	≤14 days	28 days	84 days	126 days	18 weeks
2	≤14 days	84 days	56 days	154 days	22 weeks

Subjects will be enrolled at staggered intervals to facilitate adequate safety evaluation before dosing of subsequent subjects.

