4.1 General Design

All clinical data captured will be provided in data listings. Subject disposition, demographic information, and baseline characteristics will be presented. Baseline will be defined as the last value obtained prior to the first dose of study drug. Results will be summarized by dose and dosing regimen (cohort), and in total. Any discrepancy between treatment to be given and treatment received will be accounted for in these displays.

Continuous data will be summarized using descriptive statistics: number of subjects (N), number of observations (n), mean, median, standard deviation (SD), minimum, and maximum.

Categorical data will be summarized using frequencies and percentages. When categorical data will be presented, the percent will be suppressed when the count is zero to draw attention to the non-zero counts. The denominator for all percentages, unless otherwise specified, will be the number of subjects in the specified analysis population.

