4.7.1 Adverse Events

Adverse events data will be coded using the Medical Dictionary for Regulatory Activities (MedDRA 19.1). Adverse events will be graded using the NCI CTCAE, Version 4.03.

A treatment-emergent adverse event (TEAE) is defined as any AE that starts on or after the first dose of study drug or occurs prior to the first dose and worsens in severity on or after the first dose of study drug, during the treatment period and follow-up period.

For AEs with partial start dates, non-missing date parts will be used to determine if the AE is treatment-emergent or not. If a determination cannot be made using the non-missing date parts as to when the AE occurred relative to study drug administration, e.g. AE start year and month are the same as the year and month of the first dose of investigational product, then the AE will be classified as treatment-emergent. See [Appendix B](#) for details on imputation rules.

An overview of TEAEs will be provided. The overview will summarize the subject incidence of the following information:

- Any TEAEs
- Worst NCI CTCAE grade of TEAEs
- Drug-related TEAEs
- Worst NCI CTCAE grade of drug-related TEAEs
- Any study drug-related Grade 3 or greater TEAEs
- TE-SAEs
- Drug-related TE-SAEs
- TEAE leading to discontinuation of study drug
- Drug-related TEAE leading to discontinuation of study drug
- TEAE leading to study drug interruption
- Drug-related TEAE leading to study drug interruption
- TEAE leading to study drug dose reduction
- Drug-related TEAE leading to study drug dose reduction
- Death

TEAEs will also be summarized using SOC, preferred term and severity grade based on NCI CTCAE (Version 4.03). Drug-related TEAEs will be summarized by the same manner.

The incidence and percentage of subjects with at least 1 occurrence of a preferred term will be included, using the most severe grade. The number of events per preferred term will also be summarized.

TEAEs, SAEs, and TEAEs leading to discontinuation of study drug, dose reduction or interruption will be listed. Duration of AEs will be determined and included in listings, along with action taken and outcome.

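### Adverse-event tables are by cohort only, so they cannot show whether Cohort 2 events arose during loading, maintenance or follow-up

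*SAP*

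**What the plan says.** SAP section 2.1 defines the primary safety endpoint as safety findings, including adverse-event incidence, "summarized by dose and dosing regimen, severity, and relationship to study drug".

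Section 4.1 sets the general grouping: "Results will be summarized by dose and dosing regimen (cohort), and in total". It adds: "Any discrepancy between treatment to be given and treatment received will be accounted for in these displays". No method for doing so is given.

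Section 4.7 applies that grouping to adverse events: "The incidence of AEs, TEAEs and SAEs will be summarized by cohort, severity and relationship to study product". Section 4.7.1 adds an overview table and, for the detail: "TEAEs will also be summarized using SOC, preferred term and severity grade based on NCI CTCAE (Version 4.03"). Drug-related events are handled in the same way. Nothing in 4.7.1 refers to treatment phase, dose at onset or a time window.

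The two cohorts are built differently (section 3.1). Up to 8 subjects "will receive SYNT001 10 mg/kg weekly x 5 doses (Cohort 1"). Up to 12 subjects receive "SYNT001 30 mg/kg weekly x 3 doses (Loading), followed by SYNT001 10 mg/kg every other week x 5 doses (Maintenance) (Cohort 2"). Table 1 footnote c allows the Cohort 2 loading dose to be lowered, the maintenance dose to be raised and the dosing frequency to be increased.

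**The concern.** Letting cohort stand for dose works when a cohort has one dose level. Cohort 1 does. Cohort 2 as planned has two, in a fixed order, followed by time off drug. A single Cohort 2 column therefore mixes events that began after 30 mg/kg infusions, events that began after 10 mg/kg infusions, and events that began in follow-up.

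The first primary objective is safety at different dose levels as well as regimens, and the second is to select a dose. A reader of the planned tables could not tell whether a cluster of events belongs to the loading course or to what follows. If footnote c is used, the column may not even describe one regimen.

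**Working it through.** The SAP gives no figure to reproduce here: safety is descriptive (section 4.7) and no sample size was calculated (section 5). The check compares sections and adds simple arithmetic on the planned schedule.

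**1. Which safety outputs let the reader see the dose level?**

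- Dose administered (4.6): by scheduled visit and cohort, so yes.
- Laboratory results (4.7.2): by cohort, visit and time point, so yes.
- Vital signs (4.7.3): by scheduled time point and cohort, so yes.
- Physical examination (4.7.3): by visit and dose, so yes.
- Adverse events (4.7, 4.7.1): by cohort, severity, relationship, system organ class, preferred term and grade. There is no time or dose axis, so no.

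The preferred-term table counts a subject once at the most severe grade. A loading event and a maintenance event of the same term in one subject therefore become one entry. The event count keeps both but does not date them.

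**2. What the Cohort 2 column contains** (section 3.1; Table 3)

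- Infusions with 12 subjects: 12 × 3 = 36 at 30 mg/kg and 12 × 5 = 60 at 10 mg/kg.
- Planned dose per subject: 3 × 30 = 90 mg/kg in loading and 5 × 10 = 50 mg/kg in maintenance. Loading is 90/140 = 64% of the planned amount.
- Time: Day 0 to the first maintenance dose on Day 28 is 28 of 140 days, or 20%.

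**3. What the cohort columns compare** (Tables 2 and 3)

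- Cohort 1: 5 infusions, last visit Day 112. Cohort 2: 8 infusions, last visit Day 140.
- If events occurred at one constant rate per day with no dose effect (assumption), expected events per subject would still differ by 140/112 = 1.25.

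**4. Can the merged incidence reveal the phase?** Let pL and pM be the proportions of subjects with an event in loading and in maintenance. They are assumed, taken as independent, and follow-up is ignored. Merged incidence = 1 − (1 − pL)(1 − pM).

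| pL | pM | Merged | Of 12 subjects |
|---|---|---|---|
| 50% | 10% | 55% | 6.6 |
| 10% | 50% | 55% | 6.6 |
| 40% | 10% | 46% | 5.5 |
| 10% | 40% | 46% | 5.5 |
| 30% | 30% | 51% | 6.1 |

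The formula is symmetric in pL and pM, so opposite patterns give the same table entry. Even an equal split (51%) differs from a fivefold imbalance (55%) by only about half a subject in 12.

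**5. How many regimens could one label cover?** If the options in footnote c combine freely (assumption): 3 loading doses × 3 maintenance doses × 2 frequencies = 18.

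**The case against.** The SAP chose this grouping openly. Section 4.1 equates dose and regimen with cohort, and section 4.7 applies that. Cohort 2 is one fixed-sequence regimen, and the regimen is part of what the trial seeks to select. Events and dosing are listed (4.6, 4.7.1), so with at most 12 subjects the onset of each event can be read against the infusions by hand. Table shells are left to separate documents (section 6). A phase split cannot isolate an effect of 30 mg/kg, because dose in Cohort 2 moves together with time and cumulative exposure. The dose-selection criteria are IgG and PDAI, not adverse events.

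Much of this stands, and it limits the point. Three stronger readings that a reader might infer are not supported:

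- *The primary safety endpoint is not delivered.* The endpoint names dose and regimen, and cohort delivers the regimen part. What is missing is the dose-level view within Cohort 2.
- *A loading-dose toxicity is diluted by later low-dose or off-drug time.* The planned tables report subjects with an event and event counts, neither divided by time. A subject with a loading event stays counted, and the merged incidence above is never below pL.
- *Before Day 21 the cohorts differ in dose alone.* Dose number and spacing match (Days 0, 7 and 14), but the cohorts are not described as randomized. Their caps on pemphigus foliaceus differ (3 of up to 8, against 2 of up to 12). Cohort 1 has 8 visits from Day 0 to before Day 21 (Days 0, 1, 2, 5, 7, 12, 14 and 19), against 3 in Cohort 2. More contact may bring more events to light at the lower dose.

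The listings do not remove the gap. They tabulate nothing, and no dose-at-onset variable is named. The commitment in section 4.1 to account for discrepancies does not help either: a Cohort 2 subject treated exactly as planned has no discrepancy.

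**Conclusion.** The point holds as a reporting gap of moderate size that should be closed before database lock. No number in the SAP is wrong, and the regimen comparison is provided. Within Cohort 2, however, the adverse-event tables cannot show the phase or dose level in which events began. That part of the primary safety endpoint has no planned table.

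The 55% illustration rests on assumed incidences, independence between phases and no follow-up events. The symmetry that makes opposite patterns look alike does not depend on the particular values. The count of 18 regimens assumes that the footnote c options combine freely. The gap exists even if the regimen is never modified; modification would widen it, because no grouping rule is stated.

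**What to change.** In sections 4.7 and 4.7.1, keep the cohort tables and make these additions:

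1. For Cohort 2, tabulate treatment-emergent, drug-related and Grade 3 or higher treatment-emergent events by phase at onset: Loading (first dose to before the first maintenance dose), Maintenance, and Follow-up. State where Maintenance ends, because events soon after the last infusion depend on it.
2. Give the number of subjects entering each phase, and infusions or subject-time as denominators.
3. Add to the adverse-event listing the actual mg/kg of the last infusion before onset.
4. State that subjects whose regimen was modified under footnote c are grouped by the dose actually received.
5. State how partial onset dates are assigned to a phase. Under Appendix B, a start date lacking only the day, in the month of first dose, is set to the first-dose date unless the event ended before then. It would therefore fall in Loading by rule.

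A side-by-side table of events with onset before Day 21 in the two cohorts is optional. It should be labelled descriptive, with a note that the cohorts are not described as randomized and that Cohort 1 has more visits in that window.

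The cost is SAP wording and a small set of tables from onset and dosing data already planned. The downsides are small cells, delayed events that may be counted in a later phase, and the confounding of dose with time and cumulative exposure. The cohort tables should therefore stay and the split be read descriptively.

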4.7.1 Adverse Events

Adverse events data will be coded using the Medical Dictionary for Regulatory Activities (MedDRA 19.1). Adverse events will be graded using the NCI CTCAE, Version 4.03.

A treatment-emergent adverse event (TEAE) is defined as any AE that starts on or after the first dose of study drug or occurs prior to the first dose and worsens in severity on or after the first dose of study drug, during the treatment period and follow-up period.

For AEs with partial start dates, non-missing date parts will be used to determine if the AE is treatment-emergent or not. If a determination cannot be made using the non-missing date parts as to when the AE occurred relative to study drug administration, e.g. AE start year and month are the same as the year and month of the first dose of investigational product, then the AE will be classified as treatment-emergent. See [Appendix B](#) for details on imputation rules.

An overview of TEAEs will be provided. The overview will summarize the subject incidence of the following information:

- Any TEAEs
- Worst NCI CTCAE grade of TEAEs
- Drug-related TEAEs
- Worst NCI CTCAE grade of drug-related TEAEs
- Any study drug-related Grade 3 or greater TEAEs
- TE-SAEs
- Drug-related TE-SAEs
- TEAE leading to discontinuation of study drug
- Drug-related TEAE leading to discontinuation of study drug
- TEAE leading to study drug interruption
- Drug-related TEAE leading to study drug interruption
- TEAE leading to study drug dose reduction
- Drug-related TEAE leading to study drug dose reduction
- Death

TEAEs will also be summarized using SOC, preferred term and severity grade based on NCI CTCAE (Version 4.03). Drug-related TEAEs will be summarized by the same manner.

The incidence and percentage of subjects with at least 1 occurrence of a preferred term will be included, using the most severe grade. The number of events per preferred term will also be summarized.

TEAEs, SAEs, and TEAEs leading to discontinuation of study drug, dose reduction or interruption will be listed. Duration of AEs will be determined and included in listings, along with action taken and outcome.

4.7.2 Clinical Laboratory Tests

Laboratory results, percentage change and absolute change from baseline will be summarized by cohort, visit and time point using descriptive statistics. Incidence of laboratory abnormalities and laboratory NCI CTCAE (Version 4.03) will be summarized. Shift tables of CTCAE Grade for chemistry parameters (Normal, Grade 1, Grade 2, Grade 3, Grade 4, Grade 3/4, Total, Missing) from baseline to each post-baseline time point showing number and percentage of subjects with movement between categories will be presented. The worst on-study grade after the first study drug administration will be summarized.

Baseline is defined as the Day 0 (pre-dose) measurement. If the baseline measurement is missing, the last measurement prior to the first study drug administration.

Results for variables that are not coded will be presented in the listings as below, within, and above the normal limits of the local laboratory.

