3.1.5 Clinical Laboratory Measurements

Laboratory testing (hematology, urinalysis, serum chemistry, virology, serology, pregnancy tests, PD, PK, and ADA) will be performed using established methods by a central laboratory.

Abnormalities in clinical laboratory tests that are considered clinically significant are to be recorded on the AE eCRF page. Laboratory results will be graded using the NCI CTCAE, Version 4.03.

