- b. Vital sign measurements (sitting blood pressure, heart rate, respiratory rate, and oral temperature) to be obtained after 5 minutes of seated rest. Any abnormal measurements are to be repeated after 5 minutes of rest. On Days 0, 7, 14, 21, and 28, vital sign measurements will be collected immediately prior to the infusion; 15, 30, and 45 minutes after the start of the infusion; at completion of the infusion; and 30 minutes, 1 hour, and 2 hours following completion of the infusion.
- c. Pulse oximetry: On Days 0, 7, 14, 21, and 28, pulse oximetry to be measured immediately prior to the infusion; 15, 30, and 45 minutes after the start of the infusion; at completion of the infusion; and 30 minutes, 1 hour and 2 hours following completion of the infusion.
- d. Clinical safety labs: hematology, clinical chemistry, and urinalysis (See Protocol Section 7.5 for a complete list). Full clinical safety laboratory draws will be collected at screening and on Days 0, 7, 14, 21, 28, 33, 42, 56, 84, and 112.
- e. Pregnancy test (women of childbearing potential only): To be performed at time of screening, prior to first dose of SYNT001 on Day 0, and on Days 56 and 112. Urine or serum test is acceptable; however, positive urine tests must be confirmed with serum testing.
- f. Digital 12-lead ECG to be obtained in triplicate at least 1 to 2 minutes apart and after 5 minutes of rest in a supine position. See Protocol Section 7.6 for additional information. On Days 0 and 28 to be obtained 5 minutes after the completion of infusion. Day 12 ECG will be collected only if the visit is conducted at the study site.
- g. Serology: Testing at Day 56 will not be done for any subject whose baseline titer is below the level of detection. If the Day 56 results are greater than 30% below the baseline value, or if the subject falls below the level of detection, the subject will be re-tested at Day 84; if still below the baseline value (or level of detection), the subject will be re-tested at Day 112. Any subject whose baseline value for tetanus or VZV was above the detectable level at baseline, and is not within 30% of the baseline value or is below the detectable level by Day 112, will be referred to their primary care physician for further management. See Protocol Section 7.5.3 for additional information.

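### No hematology grade shift table is planned, and the laboratory incidence and worst-grade summaries do not separate pre-existing from new or worsened CTCAE grades

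*SAP*

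**What the plan says.** Section 4.7.2 of the SAP plans four laboratory displays.

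1. Values and change: "Laboratory results, percentage change and absolute change from baseline will be summarized by cohort, visit and time point using descriptive statistics". This is not limited to any panel.
2. Incidence: "Incidence of laboratory abnormalities and laboratory NCI CTCAE (Version 4.03) will be summarized". Nothing requires the grade to be new or worse than at baseline.
3. Grade shifts: "Shift tables of CTCAE Grade for chemistry parameters", from baseline to each later time point. Hematology is not named.
4. Worst grade: "The worst on-study grade after the first study drug administration will be summarized". The baseline grade is not mentioned.

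Hematology belongs to the scheduled safety panel. Note d to Table 2 in Appendix A reads "Clinical safety labs: hematology, clinical chemistry, and urinalysis", and note d to Table 3 defines the panel in the same way for Cohort 2. Section 3.1.5 applies grading to laboratory results generally: "Laboratory results will be graded using the NCI CTCAE, Version 4.03". Section 2.1 makes clinical safety laboratory tests part of the primary safety endpoint.

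**The concern.** Hematology grades will exist at baseline and after dosing, but no planned summary cross-classifies them. In the incidence and worst-grade tables, a subject with a stable Grade 2 count from entry looks the same as a subject who went from normal to Grade 2.

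The study is open-label with no control arm, so each subject's own baseline is the main reference for a laboratory finding. Section 3.1.18 has sites record immunosuppressants, corticosteroids and transfusions from the 90 days before enrollment, and rituximab cycles from the previous 5 years. That makes some abnormal counts at entry plausible, though it does not say how many. What is at stake is whether the hematology grade tables, one component of the primary safety endpoint, can be read as showing new or worsened findings.

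**Working it through.** The SAP states no figure on this point, so there is none to reproduce. The check is mainly a comparison of text.

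**Which displays use the baseline grade or category**

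| Display | SAP section | Referenced to baseline? |
|---|---|---|
| TEAEs that began before dosing | 4.7.1 | Yes, counted only on worsening |
| ECG category | 4.7.3 | Yes, shift table |
| QTcF | 4.7.3 | Yes, worsening and increase from baseline |
| Chemistry grade, by time point | 4.7.2 | Yes, shift table |
| Hematology grade, by time point | 4.7.2 | No display planned |
| Incidence of laboratory abnormalities | 4.7.2 | No condition stated |
| Worst on-study laboratory grade | 4.7.2 | No condition stated |

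Hematology is the graded safety panel left without a grade comparison, and 4.7.2 gives no reason. A shift from baseline to worst grade is not stated for chemistry either.

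**What the tables would show.** Take subject A, Grade 2 at baseline and Grade 2 throughout, and subject B, normal at baseline and Grade 2 after dosing. Both have a worst on-study grade of 2 and both count in an unconditioned incidence table. In a table of baseline grade by worst post-baseline grade, A falls in the cell (2, 2) and B in the cell (normal, 2). Only B is a worsening.

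**Illustration of size, on an assumed rate.** Let p be the proportion of subjects who enter with a hematology value of Grade 1 or higher that persists unchanged. The SAP does not give p; I take 5% to 30%. Cohort sizes are the maxima in section 3.1: 8, 12, and 8 + 12 = 20 in total. The expected number of such subjects is n × p. The chance of at least one is 1 − (1 − p)^n, treating subjects as independent.

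| n | Expected, p = 5% | Expected, p = 30% | At least one, p = 5% | At least one, p = 30% |
|---|---|---|---|---|
| 8 | 0.4 | 2.4 | 33.7% | 94.2% |
| 12 | 0.6 | 3.6 | 46.0% | 98.6% |
| 20 | 1.0 | 6.0 | 64.2% | 99.9% |

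Each such subject would enter the worst-grade table with no worsening. The numbers show how the table would behave under the assumed rate. They do not estimate this trial's rate.

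**The case against.** Three stronger readings are tempting, and the SAP supports none of them.

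*That entry cytopenias would be reported as drug toxicity.* A reader might infer this, but the worst-grade label describes timing, not cause. The tables that attribute events to drug are the adverse event tables. There, an event that began before dosing counts only if it "occurs prior to the first dose and worsens in severity on or after the first dose of study drug". Section 3.1.5 also limits which laboratory findings become adverse events: "Abnormalities in clinical laboratory tests that are considered clinically significant are to be recorded on the AE eCRF page". By these rules an unchanged entry abnormality does not reach the TEAE or drug-related TEAE counts.

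*That hematology has no baseline reference at all.* It has one. Absolute and percentage change from baseline are planned for laboratory results without restriction, and sections 4 and 4.1 list all clinical data. With at most 8 and 12 subjects, a reader can check each case by hand. This limits the harm but does not close the gap. Means and medians by visit do not count subjects whose grade rose, and listings are not a summary. Graded changes not judged clinically significant never reach the adverse event tables, so the laboratory displays are their only planned summary.

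*That a shift table would separate drug effect from background.* It would not. It separates unchanged from worsened grades. Without a control arm, the cause of a worsening remains open, and that limit comes from the design.

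Two further objections have some weight. The worst-grade sentence follows directly after the shift-table sentence and could be read as chemistry only. On that reading hematology has even less, namely the undefined incidence summary, so the gap remains. Section 6 leaves table shells to separate documents, which could add the display. As the text stands, however, it names chemistry alone, and a programmer who follows it would omit hematology.

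**Conclusion.** The point holds in limited form. Grade shift tables are confined to chemistry, so no planned summary compares post-dose with baseline hematology grade. The incidence and worst-grade summaries, as written, mix pre-existing with new or worsened grades.

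The consequence is limited to the laboratory grade tables. TEAE counts, the dose-selection criteria and the change-from-baseline summaries are unaffected. The size is unknown, because the SAP gives no rate of abnormal counts at entry and any eligibility limits on blood counts would be in the protocol, which is not at hand. The 1 to 6 of 20 subjects above rests entirely on the assumed 5% to 30%, on persistence without change, and on full enrollment.

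This is a cheap improvement to the reporting of a descriptive safety study. It is not a flaw that would change its main conclusions.

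**What to change.** In SAP section 4.7.2:

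- Add, for each CTCAE-graded hematology and chemistry parameter, one shift table from baseline grade to worst post-baseline grade, by cohort and in total.
- Define the incidence of graded laboratory abnormalities as the number and percentage of subjects with a post-baseline grade higher than their own baseline grade.

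Visit-by-visit hematology shifts are not needed. Appendix A schedules 9 post-baseline safety laboratory visits in Cohort 1 and 10 in Cohort 2, so repeating the chemistry layout for every hematology parameter would add bulk for little gain in a study of this size. The cost is a change of SAP wording, matching table shells and a few more table pages. No additional data collection is required.
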